Surgical correction may be performed because of corneal exposure at any time during the disease, cosmetic rehabilitation usually after the disease is inactive and after other interventions such as orbital decompression or strabismus surgery are done. (14) During the active phase of the disease, it's better not to do any surgery, although patients with severe lid retraction may suffer from keratitis during this long period of exposure. Some alternatives for surgery to treat thyroid lid retraction have been postulated, such as, local guanethidine, but it was not used due to adverse side effects.(15) In another study, somatostatin or prednisolone were used for eyelid retraction; however, there was little effect in the palpebral fissure height.(16) Several reports illustrated the effects of injections with BT in thyroid lid retraction; (17-20) In some studies BT injection was done through the skin with 5-6 units in the eyelid (21, 22). In other studies injections were done through the conjunctiva with upper eyelid eversion (23, 24) with up to 10 units of BT. Some adverse effects of BT injections are entropion, ectropion, epiphora, photophobia, diplopia and ecchymosis. (25)

The purpose of this study is to see simply if eyelid position changes with a drop of BT in the eye, removing the stress and discomfort of any injections, especially important in non-cooperative patients since there have been no studies of such kind.

BT injection into the lacrimal gland has been also used to treat epiphora in patients with aberrant regeneration after 7th nerve palsy leading to crocodile tears. (26, 27). The effects of topical BT have not been studied on tear production. In our study we will use Schirmer's I test with topical anesthesia and tear meniscus height (27) to see the effect on tear production at different intervals. Also tear break up time (TBUT) and corneal fluorescein staining will be used to evaluate the ocular surface.

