#### 4) Inclusion and Exclusion Criteria\*

##### **Inclusion Criteria**

- Adults aged 18 and above that present to the oculoplastic and reconstructive surgery department that are able to provide informed consent to participate
- Presence of upper eyelid retraction or asymmetry( >1mm)

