## 5) Procedures Involved\*

*Patients coming to the oculoplastic clinic who qualify for the study based on inclusion and exclusion criteria (With upper lid retraction or asymmetry>1mm) will have the study explained to them by a research study member and they can ask questions. They will receive information on risks and benefits to research participation. For interim analysis of futility, we will do the study with BT eye drops on first 10 patients and then evaluate the results to see if there are any significant effects. If clinically significant effects are seen, then 34 patients totally (17 in BT vs 17 in saline) are included. After a written consent is obtained, External Photographs will be taken by a standard camera in standardized room light. Eyelid measurements will be done including MRD1, MRD2, PF height with the eyes in the primary position. Tear meniscus height, Schirmer I test with anesthesia and ocular staining with fluorescein will be evaluated for all patients recruited before and after eye drops are installed by the PI or resident in the clinic in the eye with greater palpebral fissure height (one eye). In each visit all these data will be obtained again. The subjects will be allocated to the treatment based on the randomization sheet provided by the biostatics department that is handed to [name], Surgical Coordinator on the 4th who will inform the PI of the patient's number. After the PI sees the patient, she will inform the resident in the clinic. The resident or the fellow in the clinic will be asked to provide the PI with the eye drop (botulinum toxin A or saline in 1 cc syringes without needles) while not informing of the contents. The research team([name], [name], [name], [name]), also blinded to the study will gather the data and take the necessary photos (double Blinded).*

*Potential toxicity or life-threatening toxicity with topical botulinum toxin is unlikely.*

*Pressure on the lacrimal sac by the patients for 2 minutes will be done to minimize systemic absorption.*

*Patients will be provided a phone number to call if any complications occur.*

*BOTOX®, JEUVEAU, XEOMIN, and DYSPORT are Crystalline preparations of BT type A, FDA approved drugs for many indications including periocular wrinkles. Saline eye drops will be also used as placebo.*

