## **Number of Subjects**

10 Patient are recruited for interim analysis of futility. If significant, then 17 patients in each group (34 total) based on power calculations for alpha of 0.05 and power of 80% per the biostatistics department.

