## **Study Timelines**

Recruitment will occur for 1 year. After interim analysis, the study will end once 34 patients are recruited. The study length for the patient is expected to be at least 3 months, with the recruitment/baseline visit and follow up visits at 3 days, 1 week, 2 weeks, 1 and 3 months from the first visit, for a total of 6 visits. The study is expected to last about 1 year from the time of IRB approval to completion of all study activities, including analysis of identifiable data.

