## Procedures Involved

**We anticipate that the procedures listed below will take about 30 to 40 minutes per patient. Each patient will have a complete ophthalmologic exam. Except as noted, the procedures below are not considered standard of care and are being conducted for the study alone.**

- A. Part 1: Pre-treatment data collection
  - External photographs, MRD1, MRD2, palpebral fissure height, tear meniscus height, Schirmer I test with anesthesia and ocular staining with fluorescein will be recorded.
- B. Part 2: Botulinum toxin or Placebo topical application
  - Subjects will be randomized to receive either 15 units of botulinum toxin A (BOTOX), incobotulinum toxin A (XEOMIN), prabotulinum toxin A (JEUVEA), the equivalent of 45 units of abobotulinum toxin A (DYSPORT) or balanced saline placebo in one eye after 10 patients are included for the interim analysis with BT eye drops topically on the surface of the eye
  - Then based on the randomization results, the examiner will apply botulinum eye drops or saline to the one of the subject's eyes.
- C. Part 3: Post-treatment data collection
  - Subjects will come back in 3 days, 1 week, 2 weeks, 1 & 3 months after they receive the treatment or control.
  - At each visit, subjects will have the measurements above again.
- D. Part 4: Data analysis
  - Data will be recorded and stored in a secure Microsoft Office Excel (Microsoft Corporation, Redmond, WA, U.S.A.) spreadsheet. Data will be graphically analyzed and represented with Adobe Photoshop (Adobe, Inc., San Jose, CA, U.S.A.).
  - Data assessed will involve assessing pre- and post-treatment MRD1 and MRD2, investigator-assessed measurements of ocular surface and tearing.
  - User performing analysis will be blinded to which eye received study drug.

Follow-up outside of the patient's next routine clinic visit will be needed for 3 days, 1 week, 2 weeks and 1 & 3 months. Patients who do have symptoms concerning any post-procedural complications will be instructed to notify study staff immediately. A phone number will be provided.

Outcomes Measures:

Primary outcome:

Outcome Measure Title: Change in palpebral fissure height

Outcome Measure Description: Palpebral fissure height will be calculated from the sum of marginal reflex distance 1 and 2 measured by the researcher.

Outcome Measure Timeframe: Baseline, day 3, 7, 14, 30 & day 90.

Secondary outcomes:

Outcome Measure Title: Change in eye ocular surface and tearing

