### **Data Analysis**

Statistical analysis will be performed by the Oculoplastic Research Laboratory research fellow. A paired t-test will be used to analyze the difference in palpebral fissure height, ocular surface and tearing. 34 subjects will be required to perform perimetric statistics.

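### The primary outcome is measured at five follow-up visits, but no single botulinum-versus-saline test is identified as the one sized at alpha 0.05

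*Combined protocol and SAP*

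**What the plan says.** The second Procedures Involved section, under Outcomes Measures, names one primary outcome: the change in palpebral fissure height, computed as MRD1 plus MRD2. Its timing is "Outcome Measure Timeframe: Baseline, day 3, 7, 14, 30 & day 90". Study Timelines gives the same schedule: "follow up visits at 3 days, 1 week, 2 weeks, 1 and 3 months from the first visit".

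The Data Analysis section gives one method: "A paired t-test will be used to analyze the difference in palpebral fissure height, ocular surface and tearing". It does not say which measurements form the pair, which visit is tested, or how the five visits are combined. Part 4 of Procedures Involved speaks of assessing lid measurements before and after treatment, which points to a within-patient comparison.

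The design is a randomised parallel-group comparison. Section 5 says that after the lead-in "then 34 patients totally (17 in BT vs 17 in saline) are included", with the drop given "in the eye with greater palpebral fissure height (one eye"). Number of Subjects says the size is "based on power calculations for alpha of 0.05 and power of 80" per cent. It gives one alpha and no split across visits.

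Withdrawal of Subjects removes from the analysis, and destroys, the data of anyone who withdraws, including those who withdraw from only some procedures.

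**The concern.** A primary outcome with a power calculation should lead to one identifiable test. Here two choices are open.

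- **Which visit.** There are five post-baseline visits and no rule for choosing or combining them. If the visit is chosen after the data are seen, or if each is tested at 0.05 and the best one is reported, the result no longer carries the 0.05 error rate used for sizing.
- **Which comparison.** Patients in the two arms are different people, so a paired t-test has no natural pair across arms. Read as a pre/post test, it does not use the saline control that the trial randomises to obtain.

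The withdrawal rule adds to this. A patient measured at whichever visit is decisive, who then withdraws before day 90, is lost even though the needed measurement exists.

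**Working it through.** **1. The plan's own figure.** The 17 per arm cannot be reproduced, because no difference in millimetres, no standard deviation and no standardised effect is given. That is a missing input, not evidence that 34 is wrong. Working backwards for a two-sided two-sample test (assumed) with 80% power, the normal formula gives d = (1.960 + 0.842) × √(2/17) = 2.802 × 0.343 = 0.96. The exact t calculation gives 0.99. Nothing in the text ties this to a particular visit.

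**2. Error rate if any significant visit counted as success.** This rule is an assumption; the documents do not contain it.

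- Inputs from the documents: 5 post-baseline visits, 17 per arm, alpha 0.05.
- Inputs assumed: two-sided tests, a between-arm two-sample t-test at each visit (32 degrees of freedom), and equal correlation between the changes at any two visits.
- Independent visits: 1 − 0.95⁵ = 0.226. This is an upper reference only, because changes from a shared baseline are unlikely to be uncorrelated.
- Correlated visits, by simulation of null data with 200,000 runs per setting:

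| Assumed correlation | Any visit significant, two-sided 0.05 |
|---|---|
| 0.5 | about 18% |
| 0.7 | about 15% |
| 0.9 | about 10% |
| 0.99 | about 6.5% |
| 1 | 5% |

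Repeat runs differ by up to about 0.3 percentage point (18.3% to 18.6% at correlation 0.5), so more decimals are not warranted.

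One reference point for the correlation: if all six measurements had equal variance and equal pairwise correlation r, then in units of that variance Cov(Yᵢ − Y₀, Yⱼ − Y₀) = 1 − r and Var(Yᵢ − Y₀) = 2(1 − r). The correlation of changes is then 0.5 for any r below 1. The documents do not show that these conditions hold from day 3 to day 90.

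Sidedness is not stated. Counting only results in the direction of benefit at the two-sided critical value gives 9.2% at correlation 0.5 and 5.1% at 0.9, against 2.5%. If the 0.05 is one-sided, the rates are 16.8% and 9.4%, against 5%.

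**3. What a pre/post test would measure.** Entry requires "Presence of upper eyelid retraction or asymmetry( >1mm"), and the treated eye is the one with the greater fissure height. Patients selected for an extreme value may change on average without any drug effect. As an illustration with an assumed background change, a paired t-test in 17 patients at a single visit has noncentrality δ√17:

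- δ = 0.2 SD of the change: 0.2 × 4.123 = 0.82, rejection rate 12.1%.
- δ = 0.3 SD: 0.3 × 4.123 = 1.24, rejection rate 21.4%.

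These values of δ have no source in the documents. They show only why the saline arm must enter the test.

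**4. Bonferroni as an alternative.** With 0.05/5 = 0.01 per visit and d = 0.99 from step 1, power at a given visit falls from 80% to 56%, and 26 per arm would be needed to restore it.

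**The case against.** The strongest reply is that no error rate has been shown to be inflated. The plan lists one primary outcome and the times at which it is measured; it does not say that any significant visit is a success. The rates in the table also belong to a two-sample test, whereas the plan names a paired one, and they depend heavily on an unknown correlation. All of that stands. A reader might infer that this trial runs at a false-positive rate near 18%. The documents do not support that, because the any-visit rule appears nowhere.

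A second reply is that this is a first look. Background says so: "The purpose of this study is to see simply if eyelid position changes with a drop of BT in the eye". The drug product section adds that the work is not meant to be submitted as a controlled study for a new indication. Reporting a time course with 17 per arm is common in such work. This lowers the stakes but does not remove the point. The investigators chose randomisation, a placebo arm, a named primary outcome and a power calculation, and these call for one test that can be pointed to.

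A third reply is that the unstated sidedness and the place of the 10 lead-in patients are separate matters. That is right, and the conclusion here does not rest on them. The withdrawal rule is different: it decides whose data enter whichever contrast is named.

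**Conclusion.** The gap is real and can be read directly from the text. There are five post-baseline visits and one alpha of 0.05, and the only test named is paired. No primary visit, no summary over visits and no botulinum-versus-saline contrast is specified. Followed as written on the pre/post reading, the plan would leave the control arm out of the primary test and discard usable data from patients who withdraw.

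The multiplicity figures describe a risk that the plan leaves open, not a property of the plan. They are conditional on an any-visit rule, between-arm tests, two-sided 0.05 and equal between-visit correlation. Under those assumptions the rate is about 18% at correlation 0.5, 10% at 0.9 and 6.5% at 0.99, and it returns to 5% only at perfect correlation. Confidence in the gap is high; the size of any inflation cannot be fixed from the documents.

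**What to change.** Before the first patient is randomised, make three text changes.

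1. In Outcomes Measures and Data Analysis, state one primary contrast: botulinum versus saline in change in palpebral fissure height, adjusted for baseline height. It may be at one named visit, or one pre-specified summary (for example the average over visits) from a repeated-measures model using all visits. The single contrast removes the multiplicity, and the between-arm form separates drug effect from background change. Baseline adjustment serves precision and corrects chance imbalance.
2. Report the remaining visits as secondary, with estimates and confidence intervals.
3. Amend Withdrawal of Subjects so that measurements taken before withdrawal stay in this analysis. This matters even with one named visit: a patient measured at a named day-14 visit who leaves before day 90 would otherwise be lost.

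One named contrast is preferable to Bonferroni over five visits, given the power loss shown above.

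Cost: text only, with no new measurements or patients. The downside is that an effect peaking at a visit other than the named one counts only as secondary evidence. A summary over visits avoids staking the test on one visit but dilutes a short-lived effect.

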#### Adverse Events and Serious Adverse Events

Treatment-emergent adverse events, defined as any event, not present prior to the initiation of the drug treatment or any event already present that worsens in either intensity or frequency following exposure to the drug treatment, will be monitored and reported throughout the study. Treatment emergent adverse scale will be graded as the following:

- Mild: Transient or mild discomfort (<48 hours) to the subject; no medical intervention/therapy required.

- Moderate: Mild to moderate limitation in activity of the subject; no or minimal medical intervention/therapy required.

- Severe: Marked limitation in activity of the subject, some assistance usually required; medical intervention/therapy required including possible hospitalization.

Serious adverse events are defined as those which result in death, hospitalization, persistent or significant incapacity or substantial disruption of the ability to conduct normal life functions (aka disability), or congenital anomaly / birth defect.

Previously reported treatment-emergent adverse effects are described further in the risks section below.

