## 3) Background

BT is a neurotoxin produced by the bacterium Clostridium botulinum and related species. (1) It prevents release of acetylcholine, a neurotransmitter from axons ending at the neuromuscular junction, causing paralysis.(2) [name] used the first documented therapeutic application of BT when he used it for strabismus by injecting it into the extraocular muscles.(4) In 1989, BT was licensed by the U.S. Food and Drug Administration for treatment of strabismus.(4) Since then, there has been massive research on BT, which has led to the addition of newer formulations with a large range of indications. To date, BT has been widely used by neurologists and cosmetic practitioners. Recently, urologists and pain specialists are increasingly using BT for various indications. Nevertheless, neurological disorders are the most common therapeutic indication of BT. (5)

The seven main types of BT are type A to G (A, B, C1, C2, D, E, F and G).(6) Types A and B can cause disease in humans but are also used for therapeutic and cosmetic etiologies.(7) The effect of BT-A on shaping the eyebrow was first reported in 1989.(8) BT injections for facial wrinkles is the most frequently performed cosmetic procedure in the United States. BT is used for the treatment of frown lines, forehead lines, and crow's feet, which are the cosmetic indications approved by the FDA. (9)

BT has a broad margin of safety (lethal dose 50% (LD50)) in humans that can reach up to 40 U/kg BW. Therefore, its cosmetic use is relatively safe. BT does not cause any long-term adverse or side effects or persistent changes at the nerve terminals and targeted muscles. (10) Some known adverse effects for BT injection use include eyelid ptosis and weakness of the muscles. Rare complications of BT injection use include dysphagia, botulism, and possibly death, usually seen in patients treated for non-cosmetic issues. (11)

Graves' ophthalmopathy (GO) or thyroid eye disease is a potentially sight-threatening ocular disease that has puzzled physicians and scientists for nearly two centuries, usually occurring in patients with hyperthyroidism or a history of hyperthyroidism.(12) The most common clinical sign of GO is upper eyelid retraction, occurring to a various extent in about 90% of the patients suffering from GO.(13) It may cause cosmetic complaints as well as functional problems due to, for example, exposure keratitis.

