##### **Exclusion Criteria**

- Adults unable to consent
- Individuals less than 18 years of age
- Prisoners
- Pregnant women.
  - o Patients will be asked if they are pregnant by research staff before participation in the study.
- Women who are breast-feeding
- Known contradictions or sensitivities to study medication
- Grossly abnormal lid margins, anatomical abnormalities
- Variable ptosis or eyelid position (e.g., myasthenia gravis, blepharospasm)
- Any ocular or systemic condition that, in the opinion of the investigator, would confound study data, interfere with the subject's study participation, or affected the subject's safety or trial parameters
- Presence of an active ocular infection
- Inability to sit comfortably for 15 – 30 minutes
- Botulinum toxin injection in the eyelids during the past 3 weeks.
- Neuromuscular disorders (e.g., Parkinson's disease or myasthenia gravis)
- Medication use known to interfere with the effects of BTX-A within the previous 1 month (e.g., aminoglycoside or benzodiazepines),
- Previous history of hypersensitivity reactions to BTX-A
- Dysfunction of tear production or secretion (e.g., meibomian gland dysfunction or Sjogren's syndrome),

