## **6) Risks to Subjects\***

The primary risks to the subjects are adverse reactions to the medication. These risks are explained to patients prior to their arrival to the oculoplastic clinic. Previously described potential adverse reactions when injecting the periocular area are dull and transient headaches with malaise, Ptosis. Severe reactions seen in injections of BT in non-periocular areas such as anaphylaxis, soft-tissue edema and dyspnea are rare in occurrence. (28) Injection of BT in neck: Hoarseness and dysphagia). (28)

All are reversible side effects. (28)

Subjects may have mild ptosis in due to botulinum eye drop but it will eventually improve. Also, the drop can be used in the opposite eye to give symmetry.

Potential psychosocial risks to subjects include time taken from their day to undergo tests, potentially missing work, and anxiety or discomfort from the eye drop instillation process. This study is not collecting sensitive information, thus no potential risk to reputation or legal risks should occur.

Subjects will be instructed to call immediately for an appointment if they notice a change in their vision, eye redness, or the development of pain in either eye. Care will be taken by all study members to prevent the occurrence of any adverse events.

There are no well-controlled studies of BT-A eye drops in pregnant women, and the risks to the fetus or embryo are unknown/unforeseen. One prior publication reported abortion or fetal malformations which have been observed in rabbits after injection (29) however, another larger prospective study found no increased risk of malformations associate with BT-A for chronic migraine during pregnancy in 45 patients (30). No studies have been performed evaluating topical BT ophthalmic solution. BT is classified as US FDA pregnancy category C. (29)

- US FDA pregnancy category C: Animal reproduction studies have shown an adverse effect on the fetus and there are no adequate and well-controlled studies in humans, but potential benefits may warrant use of the drug in pregnant women despite potential risks.

Participants will be informed of the above information and reserve the right to decline participation in the study. We will not be following pregnancy outcomes.

Unanticipated problems or complications will be reported to the IRB according to posted guidelines.

Risks of the study are listed above and will be minimized by the following:

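### The serious adverse event definition has no life-threatening criterion, so a life-threatening reaction that resolves in clinic would be reported but need not be classed as serious.

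*Combined protocol and SAP*

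**What the plan says.** The definition is in the section Adverse Events and Serious Adverse Events. It begins "Serious adverse events are defined as those which result in death, hospitalization, persistent or significant incapacity", continues with substantial disruption of the ability to carry on normal life, which a parenthesis equates with disability, and ends "or congenital anomaly / birth defect". Being life-threatening is not among the criteria.

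The same section says that all treatment-emergent adverse events are monitored and reported, and grades them Mild, Moderate or Severe. The Severe grade covers marked limitation of activity and events that need treatment, with hospitalization possible.

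Elsewhere the protocol mentions events of the kind that the definition leaves out:

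- Section 5, Procedures Involved: "Potential toxicity or life-threatening toxicity with topical botulinum toxin is unlikely".
- Section 6, Risks to Subjects: "Severe reactions seen in injections of BT in non-periocular areas such as anaphylaxis, soft-tissue edema and dyspnea are rare in occurrence".
- Section 3, Background: "Rare complications of BT injection use include dysphagia, botulism, and possibly death".

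Section 6 also sends unanticipated problems or complications to the IRB under posted guidelines, which the document does not reproduce. On pregnancy it states "We will not be following pregnancy outcomes". Pregnant women are excluded, and the stated check is "Patients will be asked if they are pregnant by research staff before participation in the study".

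**The concern.** A definition of serious events decides which events enter the serious count. Here the criteria turn on what followed the event: death, admission, incapacity or disability, or a birth defect. None asks how dangerous the event was when it occurred. A reaction that put the patient's life at risk but was reversed on the spot can therefore fall outside the definition, and the protocol itself mentions reactions of that kind.

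Section 6 says that no studies have evaluated a topical ophthalmic solution of the toxin. A later reader may therefore give weight to a statement that no serious adverse events occurred. Under the present wording that statement could be made after a life-threatening reaction.

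There is also a smaller inconsistency. Birth defect is a category of serious event, yet the protocol says that it will not follow the outcomes that would reveal one.

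**Working it through.** The point rests on wording. The plan gives no figure to reproduce and no arithmetic applies. The check is to take one case through the rule.

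**Case.** A patient has an anaphylactic reaction with dyspnea after instillation. It is treated in the clinic, and the patient recovers fully and goes home.

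| Criterion in the definition | Met? |
|---|---|
| Death | No |
| Hospitalization | No, the patient was not admitted |
| Incapacity, or substantial disruption of normal functioning | Arguable. Incapacity may be significant without being persistent, but the gloss to disability points away from a brief, reversed episode |
| Birth defect | No |

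Three criteria fail outright and the fourth depends on the investigator's reading. Two investigators could classify the same event differently and both claim to follow the protocol.

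**What happens to the event otherwise.** It is treatment-emergent, so it is recorded and reported. It required treatment, so Severe is the natural grade. The complication also goes to the IRB under section 6. The event is therefore visible in the trial's records.

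**Whether the Severe grade can stand in for the missing criterion.** It cannot. The grade measures intensity and need for assistance or treatment. It runs from events where some assistance is usual up to those that may need admission, so it takes in events that never threatened life. A count of Severe events does not identify the life-threatening ones.

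**Effect on the count.** If this were the only such event, the serious count would be 0 under a strict reading of the present wording and 1 with a life-threatening criterion.

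**Birth-defect criterion against section 6.** The definition makes a birth defect serious. Section 6 rules out following pregnancy outcomes. Pregnancy is asked about before entry, no later check is stated, and visits end at 3 months (Study Timelines). A birth defect in a pregnancy missed at entry or begun during follow-up would come to light only if someone volunteered it. If it were volunteered, it would be classed as serious. The two statements can coexist, but the protocol does not say how.

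**The case against.** The strongest reply is that little would be lost in practice. Every treatment-emergent event is reported, complications go to the IRB, and patients are given a phone number and told to notify staff at once of symptoms suggesting a complication. A reader might infer that serious harms could go unreported, but for life-threatening reactions the documents do not support that. What is at stake is the label serious. The documents attach no separate reporting timeline to that label, so no stated procedure would be missed.

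The definition is also broader than death, admission and lasting incapacity. Its wording on substantial disruption could be read to cover anaphylaxis or a transient loss of vision. That stands, and it is why the conclusion is that such an event need not be classed as serious, rather than that it is excluded. Classification should not depend on how far that phrase is stretched.

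The named reactions carry qualifiers. Anaphylaxis and dyspnea are cited as rare and from injection at non-periocular sites, botulism as rare and from injection, and life-threatening toxicity from topical use as unlikely. The documents do not present them as expected effects of the drops. This makes the event improbable but does not close the gap.

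Four further readings are tempting and should be set aside:

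- That safety is a main product of the trial. The aims and outcome measures include no safety endpoint, and no safety table is described.
- That upper confidence bounds for zero observed events show the size of the problem. Those bounds come from the number of patients treated and would be the same under a corrected definition.
- That the definition must also name threat to vision. The documents list no sight-threatening event as a risk of the drops, and section 3 links exposure keratitis to the eyelid disease. Adding it would be a preference.
- That the birth-defect category is unworkable. Pregnant women are excluded, and listing a category as serious does not promise active follow-up.

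**Conclusion.** The gap is real and is limited to classification. Followed as written, the definition lets a life-threatening reaction that ends without death, admission or disability be reported as Severe but not as serious, so the trial could truthfully state under its own rule that it had no serious adverse events. The conclusion assumes that such a reaction occurs, which the protocol calls unlikely, and that the disruption criterion is read in line with its gloss to disability. It affects no primary or secondary outcome, and no numerical size is claimed. The change is still worth making because the protocol itself mentions such events and the correction is a single phrase.

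The birth-defect point is a minor inconsistency between the definition and section 6. It needs a clarifying sentence and carries little weight by itself.

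**What to change.** In Adverse Events and Serious Adverse Events, add *is life-threatening* to the list of criteria that make an event serious.

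Reconcile the birth-defect criterion with section 6, for example by stating that pregnancy outcomes are not actively followed and that this category is captured only if spontaneously reported.

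The cost is one phrase and one sentence. Slightly more events may be classed as serious. No visit, test, treatment or outcome measure changes.
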